7.3 Primary Endpoint

The primary endpoint is the proportion of patients treated with Legalon® SIL that do not exhibit morbidity (liver transplantation,) and/or mortality (death) at the end of treatment period (96 hours).

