| 
Primary Objectives
 | 
The primary objective is to evaluate the efficacy of Legalon® SIL in preventing hepatic failure and/or death resulting from amatoxin poisoning in a phase II clinical trial.
 |

| | |
|------------------------------------------|----------------------------------------------------------------------------------------------------------------------------------------------------------------------------------------------------------------------------------------------------------------------------------------------------------------------------------------------------------------------------------------------------------------------------------------------------------------------------------------------------------------------------------------------------------------------------------------------------------------------------------------------------------------------------------------------------------------------------------------------------------------------------------------------------------------------------------------------------------------------------------------------------------------------------------------------------------------------------------------------------------------------------------------------------------------------------------------------------------------------------------------------------------------------------------------------------------------------------------------------------------------------------------------------------------------------------------------------------------------------------------------------------------------------------------------------------------------------------------------------------------------------------------------------------------------------------------------------------------------------------------------------------------------------------------------------------------------------------------------------------------------------------------------------------------------------------------------------------------------------------------|
| 
Primary endpoints
 | 
The primary endpoint is the percentage of subjects treated under this clinical trial without morbidity (liver transplantation) and or mortality (death).
 |

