| | 
approximation, a sample size of 139, provides a two-sided 95% confidence interval for proportion of subjects not meeting the outcome of interest (liver transplantation and/or death) within a half width of 5% from the observed proportion at an expected proportion of 90%.
 |
| 
Statistical Methods
 | 
Demographic and Anamnestical Data:
 
All demographic and anamnestical data will be analyzed descriptively. For quantitative variables, the descriptive summary (means, medians, standard deviation, minimum and maximum) will be calculated. For qualitative data, the corresponding absolute and relative frequencies will be determined.
 
Efficacy Analysis:
 
The primary endpoint is the proportion of subjects treated with Legalon[®] SIL that do not exhibit morbidity (liver transplantation) and/or mortality (death).
 
Proportion of subjects not meeting outcome of interest (liver transplantation and/or death) will be determined. Furthermore, the corresponding 95% confidence intervals will be determined.
 
Sensitivity Analyses:
 
Subject survival rate without hepatic transplantation and/or death will be calculated for all subjects and for each stage of disease. Moreover, the corresponding 95% confidence intervals for the rate of survival will be determined. The survival time will be described by means of Kaplan-Meier estimates.
 
Secondary endpoint (efficacy):
 
 • All quantitative secondary endpoints will be analyzed descriptively. Means, medians, standard deviations, minimum and maximum will be calculated as measures of location and dispersion. • The time to normality for AST, ALT, bilirubin, PT/INR, and creatinine, if abnormal at presentation, will be determined for all subjects and for each stage of disease by means of Kaplan-Meier estimates. 
Additional summaries -- Assessment of Emergency Liver Transplantation Criteria in ALF due to Amanita Poisoning – using Ganzert’s and Escudie’s criteria. (13a.
 
 • Number (%) of subjects without hepatic transplantation by Ganzert’s intoxication (pre-treatment) • Elapsed days between amanita poisoning and start of treatment |

| | |

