3.2 Endpoints

3.2.1 Primary Endpoints

The primary endpoint is the proportion of subjects treated with Legalon® SIL that do not exhibit morbidity (liver transplantation and/or mortality (death)).

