7.4 Secondary Endpoint (s)

The secondary endpoints of the study are:

- Proportion of patients not needing liver transplantation
- The time to normality for AST, ALT, bilirubin, PT/INR, and creatinine during the treatment period
- Number (%) of patients without hepatic transplantation by Ganzert's intoxication (pre-treatment)
- Elapsed days between amanita poisoning and start of treatment
- Number (%) of patients without hepatic transplantation by Ganzert's intoxication (during treatment)
- Number (%) of patients without hepatic transplantation by INR severity criteria (INR < 2 and ≥ 2) (during treatment)
- Number (%) of patients without hepatic transplantation by Escudie's intoxicion grade transplantation criteria (INR < 6 and ≥ 6) (during treatment)

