7.5.3 Analysis of Primary Endpoint

The primary objective of the study is to compute the survival of the patients without liver transplantation, renal failure or death during the treatment period of 96 hours. The number and proportion of patients surviving without liver transplantation, renal failure and/or death at the end of treatment period will be computed, 95% CI for the proportion of patients surviving without liver transplantation, renal failure and/or death will be computed based on Newcombe-Wilson score method.

The analysis of primary endpoint will be performed based on Full Analysis Set.

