7.5.4 Secondary/Sensitivity Analyses for Primary Endpoints

As a sensitivity analysis, the primary analysis will be repeated using the Per-Protocol Set.

In addition, the survival rates using Kaplan-Meier estimation method at 96 hours (end of treatment period) will be computed for the patients surviving without liver transplantation, renal failure or death. 95% CI will be computed for the survival rate by using Greenwoods formula. This analysis will be carried out using both Full Analysis and Per-Protocol Analysis sets.

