7.5.7 Analysis of Secondary Endpoint(s)

All secondary analysis will be carried out using the Full Analysis Set.

The endpoints of proportion of patients not needing liver transplantation, without hepatic transplantation by Ganzert's intoxication (pre-treatment), without hepatic transplantation by Ganzert's intoxication (during treatment), without hepatic transplantation by INR severity criteria (INR < 2 and ≥ 2) (during treatment), without hepatic transplantation by Escudié's intoxication grade transplantation criteria (INR < 6 and ≥ 6) (during treatment) will be analyzed in the same way as the analysis of primary endpoint. The number and proportion of patients meeting the criteria will be computed and presented along with 95% CI that is computed using Newcombe-Wilson score method.

Elapsed days between amanita poisoning and start of treatment will be summarized descriptively.

The time to normality for AST, ALT, bilirubin, PT/INR, and creatinine will be analyzed using Kaplan-Meier estimation method of estimation for the survival time. 95% CI will be computed for the survival rate by using Greenwoods formula. The analysis of time to normality for AST, ALT, bilirubin, PT/INR, and creatinine will be analyzed by the disease severity stages as well.

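### Section 7 stops the primary endpoint at 96 hours while the synopsis and Section 3.2.1 set no cut-off, so a later death or transplant counts as a success

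*Combined protocol and SAP*

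**What the plan says.** Three places in the statistical section fix a time point. Section 7.3 counts patients who "do not exhibit morbidity (liver transplantation,) and/or mortality (death) at the end of treatment period (96 hours". Section 7.5.3 computes survival "without liver transplantation, renal failure or death during the treatment period of 96 hours". Section 7.5.4 states that "the survival rates using Kaplan-Meier estimation method at 96 hours (end of treatment period) will be computed".

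Elsewhere the endpoint has no time point. The synopsis reads: "The primary endpoint is the percentage of subjects treated under this clinical trial without morbidity (liver transplantation) and or mortality (death". Section 3.2.1 reads: "The primary endpoint is the proportion of subjects treated with Legalon® SIL that do not exhibit morbidity (liver transplantation and/or mortality (death". The synopsis sensitivity analysis is also undated: "Subject survival rate without hepatic transplantation and/or death will be calculated for all subjects and for each stage of disease". The interim summary in Section 7.6 gives the endpoint as no transplant or death, again without a cut-off, and scores its 42 successes by discharge home with recovery.

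The 96-hour mark does not end treatment for everyone. The synopsis allows a longer course after consultation with the primary principal investigator. The synopsis methodology text and Sections 4.3.4 and 6.3 place the discussion of patients who are not improving at about 96 hours or later.

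**The concern.** A patient who is alive with the native liver at hour 96 and dies on day 7 is a success under Section 7.3. Under the synopsis or Section 3.2.1, read naturally, the same patient is a failure. The trial's single primary result therefore depends on which section the analyst follows.

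The cut also falls at an awkward moment. By the protocol's own account, 96 hours is when the investigators decide what to do about patients who have not improved, and some of them go on to extended treatment. A death or transplant during that extended treatment, or between its end and the Follow-up Visit, lies outside the Section 7 endpoint, although the protocol already schedules a visit to observe outcome after treatment.

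**Working it through.** **Step 1: the plan's own figure.** Section 7.1 gives 139 subjects for a two-sided 95% interval with half-width 5% at an expected proportion of 90%, by the normal approximation.

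- n = 1.96² × 0.90 × 0.10 / 0.05² = 138.3, rounded up to 139.
- Half-width at 139 = 1.96 × √(0.09/139) = 4.99%.

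The figure reproduces. The formula has no time term, so the cut-off does not make N wrong.

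**Step 2: what falls outside the endpoint.** Take a course of exactly 96 hours (4 days).

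- With the visit at 10 ± 2 days after last dose (synopsis, 2.2, 6.4), it falls 4 + 8 = 12 to 4 + 12 = 16 days after first dose. The uncounted interval is 8 to 12 days.
- With the 7 to 14 day window of Section 4.1, it falls at day 11 to 18, and the uncounted interval is 7 to 14 days.
- For a longer course, the days of treatment after hour 96 are added to the uncounted interval.

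The last line takes the cut at hour 96, which the wording of 7.5.3 and 7.5.4 favours. If end of treatment period meant the actual end of drug, events on extended treatment would count, but those between last dose and the visit would still be missed.

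**Step 3: direction.** On the 7.3 composite (death or transplant), lengthening the horizon can only turn successes into failures. The early cut can therefore only raise the rate or leave it unchanged.

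**Step 4: size, by assumption.** Section 7.6 reports 42 successes and 8 failures (5 deaths, 3 transplants) in 50 patients: 42/50 = 84%. It gives no event times. If k of the 8 failures fell after the cut, the 7.3 rate would be (42 + k)/50, or 2 points per late event. For illustration, k = 0 gives 84%, k = 1 gives 86% and k = 3 gives 90%. In the full trial each late event is worth 1/139 = 0.72 points.

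**Step 5: the renal component.** Sections 7.5.3 and 7.5.4 add renal failure, which 7.3 and the interim did not count. The rate becomes (42 + k − r)/50, where r is the number of interim successes with renal failure before the cut and k now counts only late failures without earlier renal failure. With assumed k = 3 and r = 3 the result is 45/50 − 3/50 = 84%, no net change. The net shift against the interim has no known sign.

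**Step 6: does another planned analysis recover the late events?**

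- The Per-Protocol repeat and the Kaplan-Meier estimate in 7.5.4 inherit the cut.
- The synopsis survival rate in the sensitivity analyses states no horizon and is supportive only.
- The secondary endpoint "Proportion of patients not needing liver transplantation" (7.4) leaves out deaths, and 7.5.7 says it "will be analyzed in the same way as the analysis of primary endpoint" without saying whether the cut applies.
- Sections 7.7.1 and 9.1.1 collect adverse events to 30 days after last dose, and SAEs are listed. Late deaths may be visible there but do not enter the primary rate.

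**The case against.** Section 7 is largely consistent on hour 96, and a synopsis that omits a time point may simply be less specific. A 96-hour landmark can be a legitimate choice, and late deaths would not vanish, since fatal events are SAEs and are listed. Changing the horizon now would also mean choosing it after the open-label outcomes of 50 patients were known, and later status may be hard to obtain for patients seen at ad hoc sites and followed by local physicians.

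Part of this stands. The safety listings are a real mitigation, and the timing of the change is a real cost. But no rationale for the landmark is given, the objectives section and the interim summary omit it, and a safety listing does not correct a primary proportion.

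A reader might go further in four ways that the documents do not support.

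- That the interim rate could become 100% under the cut. This needs all 8 failures to be late, and nothing gives their times. The 96 hours in Section 7.6 runs from poisoning to start of treatment, a different clock: for a patient who started that late, hour 96 of treatment is more than 8 days after ingestion.
- That hospital stays of under 8 days show late failures. That remark concerns successes and hospitalization, not failures timed from first dose.
- That the final rate must exceed the interim rate. The added renal component pulls the other way.
- That the sample size is wrong. It reproduces.

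**Conclusion.** The point holds as an inconsistency in the time point of the primary endpoint, with a one-sided effect on its death and transplant components. As Section 7 is written, failures after 96 hours are scored as successes even when they occur on extended treatment or before the scheduled Follow-up Visit.

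The size cannot be fixed from the documents. The 2 points per late interim event is conditional arithmetic, not an estimate, and it applies to the 7.3 composite only. The conclusion assumes that an undated endpoint in the synopsis and 3.2.1 covers at least the planned follow-up, which is the natural reading. This should be settled before the final analysis, because the headline proportion depends on it.

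**What to change.** 1. Reconcile the follow-up windows first: 10 ± 2 days after last dose (synopsis, 2.2, 6.4), about 10 days after discharge (synopsis methodology), 7 to 14 days after discontinuation (4.1), and within 10 days of stopping (6.3.2).
2. By protocol amendment, as Section 7.5 requires for major changes to the primary endpoint, use one time point in the synopsis, 3.2.1, 7.3, 7.5.3 and 7.5.4. Any death or liver transplantation from first dose through the Follow-up Visit is a failure, taken from the visit, the hospital record or an SAE report. Use the same horizon for the Kaplan-Meier analysis, censoring at last known contact.
3. If a fixed day from first dose is preferred, choose it after step 1. Under the 7 to 14 day window, Day 30 covers courses up to 30 − 14 = 16 days and Day 20 up to 20 − 14 = 6 days.
4. Keep status at 96 hours from first dose as a secondary summary.
5. Add a sensitivity count with unknown status at the horizon as failure, since 7.5.5 does not impute in general.
6. Separately, settle whether renal failure belongs to the composite (7.5.3 and 7.5.4 against the synopsis, 3.2.1 and 7.3), and reconcile the 96-hour label with the passages on treatment duration.

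No added status check and no change in N are needed. The costs are an amendment with ethics submission, a possibly less favourable rate, and some subjects, including those already enrolled, whose later status is unknown. The horizon would also be set after open-label interim outcomes were known, so the same rule must apply to all subjects and the report must disclose when the change was made.

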7.4 Secondary Endpoint (s)

The secondary endpoints of the study are:

- Proportion of patients not needing liver transplantation
- The time to normality for AST, ALT, bilirubin, PT/INR, and creatinine during the treatment period
- Number (%) of patients without hepatic transplantation by Ganzert's intoxication (pre-treatment)
- Elapsed days between amanita poisoning and start of treatment
- Number (%) of patients without hepatic transplantation by Ganzert's intoxication (during treatment)
- Number (%) of patients without hepatic transplantation by INR severity criteria (INR < 2 and ≥ 2) (during treatment)
- Number (%) of patients without hepatic transplantation by Escudie's intoxicion grade transplantation criteria (INR < 6 and ≥ 6) (during treatment)

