| | 
More than 90% of all fatal mushroom poisonings worldwide are due to amatoxin containing species that grow abundantly in Europe, South Asia, and the Indian subcontinent. Many cases have also been reported in North America (1,2,3). Initial symptoms of abdominal cramps, vomiting, and a severe cholera-like diarrhea generally do not manifest until at least six to eight hours following ingestion and can be followed by renal and hepatic failure. Outcomes range from complete recovery to fulminant organ failure and death which can sometimes be averted by liver transplant.
 
Epidemiological data on mushroom poisoning, particularly poisoning with amatoxin-containing mushrooms, are rare. The true incidence of this intoxication is unknown since national data banks maintained at poison control centers have only incomplete data of this non-reportable illness [4].
 
Uncontrolled European studies and emergency use in the USA, suggest that treatment of amatoxin poisoning with Legalon® SIL drug may prevent severe morbidity (hepatic failure) and mortality.
 
This is a Phase II Multi-Center Open-Label Clinical Trial to Assess the Prevention of Liver Transplantation and/or Death Among Subjects Treated with Intravenous Silibinin (Legalon® SIL) for Amatoxin Induced Hepatic Failure. A total of 139 subjects will be enrolled into this study.
 
Legalon® SIL is formulated as a sterile lyophilisate in rubber-stoppered vials to be dissolved for intravenous infusion, containing 528.5 mg silibinin-C-2',3-dihydrogen succinate, disodium salt which is equivalent to 350 mg of silibinin according to DNPH testing or 315 mg of silibinin according to HPLC determination. The recommended daily dose is 20 mg silibinin/kg via continuous infusion over 24 hours, following a single loading dose of 5 mg silibinin/kg on the first day of treatment.
 
Subjects will be screened for eligibility and, if confirmed to meet the study criteria, will be enrolled to receive treatment of Legalon® SIL.
 
The study is comprised of a screening period of up to 24 hours from the time a potential study participant is identified. Treatment may be administered for up to 96 hours, or longer, following consultation with PPI. The final study assessment (Follow-up Visit) is to occur at 10 (+/-2) days from the last administered treatment. During screening, treatment and follow-up, assessments for medical history (only at screening), vital signs, labs and physical examination will be completed. Concomitant medications and adverse events will be recorded on every subject from the time of consent through the completion of the Follow-up Visit. Sponsor should be notified of any SAEs reported to the site and up to 30 days after discontinuation of study medication.
 |

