1 STUDY SCHEDULE OF ACTIVITIES

The Schedule of Activities table provides an overview of the protocol visits and procedures. Refer to the Study Conduct Section (6) for detailed information on each procedure and assessment required for compliance with the protocol.

Table 1 Study Schedule

Schedule of Events

| PHASE | SCREENING PHASE | | Dosing | TREATMENT PHASE | | FOLLOW-UP PHASE |
|------------------------------|----------------------------|------------------|--------|---------------------------------------------------------------------------|---------------------------------------------|-----------------|
| | Screening/ Presentation | Pre -First dose* | | Every 6 hours post first dose until discharge or as indicated (+/-1 hour) | Every 24 hours post first dose (+/-2 hours) | |
| Informed consent | X | | | | | |
| History | X | | | | | |
| Physical/ Review of Systems | X | X | | | X | X |
| Vital Signs | X | X | X | | | X |
| CBC, Differential, Platelets | X | X | X | | | |
| Transaminases (AST, ALT) | X | X | X | | | X |
| ALP | X | X | X | | | X |
| Ammonia | X | X | X | | X | X |
| Lactate | X | X | X | | | |
| Amylase | X | X | X | | | X |
| Lipase | X | X | X | | | X |
| Bilirubin (total) | X | X | X | | X | X |
| PT | X | X | X | | X | X |

| PHASE | SCREENING PHASE | | TREATMENT PHASE | | | FOLLOW-UP PHASE |
|--------------------------------------------------------------------------------------------------------------------------|----------------------------|------------------|-----------------|---------------------------------------------------------------------------|---------------------------------------------|-------------------------------------------------------------|
| | Screening/ Presentation | Pre -First dose* | Dosing | Every 6 hours post first dose until discharge or as indicated (+/-1 hour) | Every 24 hours post first dose (+/-2 hours) | |
| Event | | | | | | At Follow-up, 10 (+/- 2) Days after study drug discontinued |
| INR | X | X | | X | | X |
| BUN, Creatinine, GFR | X | X | | X | X | |
| Glucose | X | X | | X** | X | |
| Electrolytes (NA, K, Cl, CO2) | X | X | | X | | |
| Serum Pregnancy test for woman of child bearing potential | X | | | | | |
| Loading dose Legalon-SIL 5mg/kg IV over 1 hour followed by continuous IV infusion of 20 mg silibinin/kg over 24 hours | | | X | | | |
| Adverse Events | X | X | X | X | X | X |
| Concomitant Medications | X | X | X | X | X | X |

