3.2.2 Secondary Efficacy

Efficacy as demonstrated by time to normality of the laboratory values from start of treatment with Legalon® SIL. The laboratory values to be followed are transaminases and renal function tests (AST, ALT, bilirubin, PT/INR, creatinine, lactic acid).

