Conclusions: Since silibinin strongly inhibits the hepatocyte uptake of amatoxin and the survival has been correlated with the time of initiation of therapy, Legalon® SIL treatment should be instituted as soon as a diagnosis has been made/suspected. As a matter of fact, all the patients who started treatment with the study drug >96 hours after poisoning had a negative outcome.

As long as renal function has been maintained with aggressive intravenous hydration, patients who receive intravenous Legalon® SIL appear to recover from amatoxin induced hepatotoxicity in a rapid, predictable, and reliable manner. Length of hospitalization for the successfully treated patients was relatively short, often well under 8 days. Legalon® SIL was not associated with any serious adverse events. It was easy to administer, safe, and was well tolerated in this patient population.

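### Time to normality has conflicting observation windows (7.4 against 3.2.2 and the synopsis), and its Kaplan-Meier analysis makes no provision for death or transplant

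*Combined protocol and SAP*

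**What the plan says.** Section 7.4 lists as a secondary endpoint "The time to normality for AST, ALT, bilirubin, PT/INR, and creatinine during the treatment period". Section 3.2.2 describes the same measure as "time to normality of the laboratory values from start of treatment", with no end. The synopsis (Statistical Methods) also gives no end, and restricts the analysis to values abnormal at presentation. Sections 7.4 and 7.5.7 do not repeat that restriction.

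The length of the treatment period varies by section. Section 7.5.3 has "during the treatment period of 96 hours", and 7.3 also fixes 96 hours. The synopsis says "Treatment may be administered for up to 96 hours, or longer, following consultation with PPI". The Follow-up Visit is a separate phase in Table 1, headed "At Follow-up, 10 (+/- 2) Days after study drug discontinued", and AST/ALT, bilirubin, PT and INR are marked there. Creatinine is not.

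Section 7.5.7 analyses time to normality by Kaplan-Meier with Greenwood intervals, overall and by severity stage. It gives no event, censoring or competing-event rule for death or transplantation. Section 7.5.5 says only that missing data are generally not imputed and that the SAP may add detail.

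**The concern.** There are two separate problems.

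The first is the window. The stop rule (synopsis, Methodology; 6.3) allows the drug to end with AST and ALT at up to twice the upper limit of normal, and it does not mention bilirubin or creatinine. Recovery can therefore be completed after treatment, and under 7.4 the follow-up blood drawn to confirm it cannot count toward the endpoint. Two programmers could also build different datasets from the same protocol.

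The second is the estimator. A patient who dies or is transplanted can no longer normalize with the native liver. Ordinary censoring treats that patient as still able to, at the same rate as those who remain. The resulting curve is too high, and the error is larger where failures are more frequent, which is where the by-stage curves would be read most closely.

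**Working it through.** **The documents' own figures.** No figure is given for this endpoint. The nearby ones reproduce:
- Sample size (7.1): 1.96² × 0.90 × 0.10 / 0.05² = 138.3, rounded up to 139.
- Interim result (7.6): 42/50 = 84.0% recovered; 5 deaths + 3 transplants = 8/50 = 16% failed.

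**Window.** I take normal to mean within the institution's reference range; 7.4 and 7.5.7 do not define it.
- *Fixed 96 hours (7.3, 7.5.3).* This is an administrative cut. It does not bias the curve up to 96 hours, but later recoveries are lost.
- *Actual infusion (synopsis).* Censoring at drug stop is informative. Patients who stop by meeting the rule are close to normal; patients stopped for lack of improvement after 96 hours (4.3.4) are not. Neither group resembles those still being infused.
- *Table 1 treatment phase.* One of its columns runs to discharge, so a third sense is possible.

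Follow-up lies outside all three. The documents give no rate at which the laboratory values fall, so the number of recoveries missed cannot be calculated.

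**Death and transplant.** Let f be the proportion failing and c the true proportion normalized (cumulative incidence) by the cut, with no other censoring. The excess is the Kaplan-Meier estimate of normalization, with failures censored, minus c.
- All failures before any recovery: estimate = c/(1 − f), so excess = c × f/(1 − f).
- Failures and recoveries in random order: estimate ≈ 1 − (1 − c − f)^(c/(c + f)).

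Inputs: f = 16% (interim, 7.6) and f = 10% (the complement of the 90% expected in 7.1). The values of c are assumptions.

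| f | c | Excess, failures first | Excess, random order |
|---|---|---|---|
| 10% | 10% | 1.1 points | 0.6 |
| 10% | 20% | 2.2 | 1.2 |
| 10% | 40% | 4.4 | 2.6 |
| 16% | 10% | 1.9 | 0.9 |
| 16% | 20% | 3.8 | 2.0 |
| 16% | 40% | 7.6 | 4.4 |

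For f = 16% and c = 20%:
- Failures first: 0.20 × 0.16/0.84 = 0.038.
- Random order: 1 − 0.64^(0.20/0.36) = 0.220, an excess of 0.020.

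**Check by counting.** Take 50 patients, with 8 failing first and 10 then normalizing. Censoring gives 10/42 = 23.8%; the true proportion is 10/50 = 20.0%. Keeping the 8 at risk as never normal until the cut also gives 20.0%.

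**Limiting case for a longer window.** If all 42 non-failures had normalized by follow-up, censoring would give 42/42 = 100% against a true 42/50 = 84%, an excess of 16 points. Extending the window without changing the estimator would therefore enlarge the error.

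**The case against.** The strongest defence has four parts.

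1. *Follow-up values are not lost.* A reader might infer that these blood draws are wasted on any reading of the protocol. The documents do not support that. Sections 3.2.2, 7.5.7 and the synopsis set no end, so follow-up values could count there. Section 7.7.4 summarizes laboratory results by timepoint in any case. What stands is a conflict in the definition of this endpoint, and a summary by timepoint does not supply a time to normality.

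2. *Detail is deferred.* Section 7.5 leaves methodology to a SAP whose text is not supplied, and nothing in 7.5.7 says that failures are censored. That is fair, and the overstatement is conditional on ordinary censoring. But the window and the estimator are already written into the protocol, and ordinary censoring is what a bare Kaplan-Meier instruction invites.

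3. *A short window is defensible.* Follow-up is one late draw, patients who go to transplant are exempt from it (6.4), creatinine is not drawn, and PT/INR normality is already part of the stop rule. The window therefore matters mainly for AST, ALT and bilirubin, and a late draw shows only that normality was reached at some point since the previous draw. This shapes the remedy, but it does not reconcile 7.4 with 3.2.2.

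4. *The size is easily overstated.* The 16% covers the whole clinical outcome and is not a 96-hour rate; failures after the cut do not compete within it. A reader might also infer a gross distortion from the 90% probability of death given for Grade 4 in the background. But 7.5.7 plans curves by severity stage, and the background places Grades 3 and 4 together under Stage III, so no separate Grade 4 curve is shown to be planned. The documents give no failure rate by stage.

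**Conclusion.** The point holds and is minor. Section 7.4 conflicts with 3.2.2 and the synopsis on the observation window, and the treatment period that 7.4 relies on has more than one meaning. On the infusion reading, censoring at drug stop is informative. Section 7.5.7 names an estimator that overstates normalization if deaths and transplants are censored in the ordinary way: about 2.0 points, and at most 3.8, at 16% failures with 20% normalizing. Those sizes rest on an assumed share normalizing and on applying the whole-outcome interim rate within the window, so they illustrate scale and are not predictions. The excess rises with the failure rate, so it is larger in the more severe stages, but the documents do not allow a figure there. The endpoint is descriptive, and neither the primary analysis nor N = 139 is affected.

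**What to change.** 1. State one window in the synopsis, 3.2.2, 7.4 and 7.5.7: from start of treatment through the Follow-up Visit for tests drawn there, and through the last scheduled draw for creatinine. Say that normal means within the institution's reference range. Because one late draw gives only interval-censored times, report the proportion normal at follow-up alongside the inpatient curve.
2. Replace Kaplan-Meier with cumulative incidence of normalization, overall and by stage, with death and transplantation as competing events and post-transplant values excluded. With a fixed cut and no other censoring, keeping these patients at risk as never normal until the cut is equivalent.
3. Carry the restriction to values abnormal at presentation into 7.4 and 7.5.7. At the same time, settle whether lactic acid belongs to the endpoint: 3.2.2 lists it, 7.4 and 7.5.7 do not.

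The cost is low: SAP text, aligned protocol wording and modest programming. Section 7.5 allows the SAP to modify these plans and commits to a protocol amendment only for major changes to the primary endpoint or its analysis. No draws beyond Table 1 and no change to the stop rule are needed. The drawbacks are that follow-up values come from local laboratories and are interval-censored.

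The follow-up provisions must be reconciled first. The visit is 10 (±2) days after last treatment in the synopsis and Table 1, about 10 days after discharge elsewhere in the synopsis, and 7 to 14 days after stopping the drug in 4.1. Table 1 includes bilirubin at follow-up, whereas the synopsis (Methodology) and 4.3.4 name only transaminases and PT/INR.
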